19.2 Randomization

This study is a randomized within-subject cross-over study, where the order of *four types of nicotine solutions* that the participant receives will be randomized. Participants will be provided with cartridges of maximum available amounts of nicotine (labeled as high: approx. 24 mg). All participants and study personnel will be blinded to the flavor names and nicotine content in cartridges. Participants will be provided with cartridges of different nicotine solutions at each visit, instructed on how to use the product, and partake in the controlled 10-minute puffing session (1 puff every 30 seconds, 20 puffs total).

Note: In order to minimize any carry-over effect, there will be a minimum 5-7-day wash-out period between each scheduled study visit and, the order of the nicotine solutions will be randomly assigned (with a different randomization order for each participant). In addition, we will consider linear mixed models that will incorporate a carry-over effect. This will provide a more conclusive analysis, but also potentially validate the effectiveness of the wash-out period, which could help in the design of future studies.

Roswell Park Protocol No.: I 475819

19.3 Demographics and Baseline Characteristics

Descriptive statistics (as appropriate: n, percent, mean, median, min and max) will be used to summarize demographic and baseline characteristics.

19.4 Primary Analysis

The primary objective is to evaluate whether AUC nicotine, C_{max} or T_{max} differ between free-base and salt-based versions of the same liquid, controlling for flavoring and nominal nicotine concentration.

Each outcome will be modeled as a function of base (free-base versus salt-based), flavor (tobacco versus unflavored), their interaction, prior combination indicator (for carry-over effect), and a random subject effect using a linear mixed model. All model assumptions will be verified graphically and transformations will be applied as appropriate. The effect of “base” on the AUC nicotine, C_{max} and T_{max} measures will be evaluated using tests about the least square means of “base”. Additionally, 95% confidence intervals about the mean differences will be obtained.

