1.1 Primary Objective(s)

- Determine whether C_{max} or T_{max} differ between free-base and salt-based versions of the same liquid, controlling for flavoring and nominal nicotine concentration [main effect of salt]
- Determine whether the effect of flavoring on subjective effects (e.g., harshness, liking) differs between matched free-base and salt-based e-liquids [flavor X salt interaction]

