8 STUDY ENDPOINTS

8.1 Primary Endpoint(s)

- Maximum concentration of nicotine in plasma (C_{max}), the area under the concentration – time curve from 0 to 120 min (AUC), and the time to maximum concentration (T_{max}).

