8.2 Secondary Endpoint(s)

- Perceived harshness, satisfaction, liking, and relief of nicotine withdrawal symptoms.

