19 STATISTICAL PLAN

19.1 Sample Size Determination

The sample size calculations are based on the primary analysis of the area under plasma nicotine concentration-time curve (AUC nicotine), which is compared between salt and free-base forms of e-liquid. A simplified calculation is based on the two-sided two-sample t-test, where a sample size of n=18 provides 80% power (at a significance level of 0.05) to detect a true difference of at least 700 ng/mL × min. This is based on the assumption that the within-patient standard deviation of the response variable is 500 ng/mL × min.

The reduction in AUC of 700 ng/mL × min corresponds to 4-fold reduction in nicotine content in tobacco cigarettes. This effect was observed among smokers who switched from cigarettes with high nicotine content (12 mg) to low nicotine content cigarettes (4 mg)

To account for potential drop-out, a maximum of 20 participants will be enrolled. Accrual for this study is expected to take 4 years.

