19.5 Secondary Analysis

The secondary objective is to evaluate the effect of flavoring on subjective effects (i.e. perceived harshness, satisfaction, liking, and relief of nicotine withdrawal symptoms) differences between matched free-base and salt-based e-liquids.

Each outcome will be modeled as a function of base, flavor, their interaction, prior combination, and a random subject effect using a linear mixed model. All model assumptions will be verified graphically and transformations will be applied as appropriate. An F-test about the interaction-term of base and flavor will be used to determine whether the impact of flavor on these subject measures differs between bases.

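### Section 1.1 disagrees with sections 8 and 19 on what is primary, and section 19.4 tests three PK outcomes with no order or adjustment, so the chance of a false-positive PK finding is about 8-14%, not 5%

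*Combined protocol and SAP*

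**What the plan says.** The statements about what is primary, all in the current text of the combined protocol and SAP:

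- **Section 1.1, Primary Objective(s).** First objective: "Determine whether C_{max} or T_{max} differ between free-base and salt-based versions of the same liquid". Second objective: "Determine whether the effect of flavoring on subjective effects (e.g., harshness, liking) differs between matched free-base and salt-based e-liquids". AUC is not mentioned.
- **Section 8.1, Primary Endpoint(s).** Three outcomes: Cmax, AUC over 0-120 minutes, and Tmax.
- **Section 8.2, Secondary Endpoint(s).** "Perceived harshness, satisfaction, liking, and relief of nicotine withdrawal symptoms".
- **Section 19.1, Sample Size Determination.** "The sample size calculations are based on the primary analysis of the area under plasma nicotine concentration-time curve (AUC nicotine"). The calculation is a "two-sided two-sample t-test, where a sample size of n=18 provides 80% power (at a significance level of 0.05").
- **Section 19.4, Primary Analysis.** "The primary objective is to evaluate whether AUC nicotine, C_{max} or T_{max} differ between free-base and salt-based versions of the same liquid". Each outcome gets its own linear mixed model, its own test of the base effect, and a 95% confidence interval.
- **Section 19.5, Secondary Analysis.** "The secondary objective is to evaluate the effect of flavoring on subjective effects", with an F-test of the base-by-flavor interaction for each subjective outcome.

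No section gives a testing order, a multiplicity adjustment, or one PK outcome that takes precedence in the analysis.

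**The concern.** Depending on the section, the primary PK question rests on two outcomes (1.1), three outcomes (8.1, 19.4) or one (19.1), and the interaction is either primary (1.1) or secondary (8.2, 19.5). A reader of the final report could not tell from the plan which result answers the primary question.

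The wording in section 19.4 joins the three PK outcomes with *or* and tests them separately. A difference on any one of them could then be reported as an affirmative answer to the primary objective. The 0.05 level and the 80% power in section 19.1 belong to a single AUC comparison. They do not carry over to a claim that any of three tests can support. Cmax, Tmax and the interaction have no power statement. Unless the order is fixed before unblinding, the deciding outcome could be chosen after the results are seen.

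**Working it through.** **1. Reproduce the plan's own figure.** Inputs from section 19.1: difference 700 and SD 500 ng/mL × min, two-sided 0.05, 80% power, two-sample t-test.

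- Normal approximation: n per group = 2 × (1.960 + 0.842)² × (500/700)² = 8.01, rounded up to 9. Two groups give 18, as stated.
- Exact noncentral-t power with 9 per group is 79.6%.

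The 18 therefore reproduces for its stated simplified test. It covers AUC only.

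**2. Level per test.** Section 19.4 states none. Two-sided 0.05 is inferred from the 0.05 in section 19.1 and the 95% intervals in section 19.4.

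**3. Chance of at least one false-positive PK result when base has no effect on any of the three.**

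- Independent tests: 1 − 0.95³ = 0.143.
- Correlated tests: simulated from 1,000,000 multivariate normal draws, counting any |z| > 1.96. The documents give no correlations, so these are assumed.

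| Assumed correlation between test statistics | At least one of three |
|---|---|
| All independent | 14.3% |
| AUC-Cmax 0.7, Tmax independent | 12.9% |
| AUC-Cmax 0.8, Tmax independent | 12.4% |
| AUC-Cmax 0.9, Tmax independent | 11.8% |
| All three 0.8 | 9.8% |
| All three 0.9 | 8.3% |

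A check with t-tests on 20 subjects agrees: 14.3% for independence, and 12.5% with AUC-Cmax 0.8 and Tmax correlated 0.2 with both.

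**4. What error control would cost.**

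- *Fixed order, AUC first.* AUC is tested at 0.05 and each later outcome only if the one before it succeeds. The error rate across the three is at most 5%, and AUC power stays at 79.6% under the plan's formula.
- *Holm across three.* The strictest step is 0.05/3 = 0.0167. With 9 per group, the plan's formula gives 62.1% power for AUC at that level, and 80% would need 13 per group (26).
- *Holm in the crossover as designed.* Section 19.1 describes 500 as a within-patient SD. Per subject, the base effect is the mean of two salt sessions minus the mean of two free-base sessions. Its variance is 500² × (1/2 + 1/2) = 500², so its SD is 500. With 18 completers, the noncentrality is 700 / (500/√18) = 5.94, and power at 0.0167 is 99.9%. This makes no allowance for the carry-over term in the model.

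**The case against.** The strongest reply is that sections 8 and 19 largely agree with each other and section 1.1 is the outlier. AUC is a primary endpoint in section 8.1 and is named first in section 19.4. Sizing a trial on one of several primary endpoints is not a contradiction in itself. Section 9 calls the trial a pilot. Section 19.4 gives an estimate and interval for every outcome, and it sets no rule that one significant result makes the trial positive.

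Much of this stands. A reader might infer from section 1.1 that AUC has no place in the primary objective at all. The documents do not support that, because AUC is absent from section 1.1 only. The pilot label lowers the stakes. It does not settle which section governs, and the plan still sets a 0.05 level and 80% power and schedules formal tests.

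A reader might also add the four subjective outcomes of section 8.2 to the three PK tests and quote a false-positive rate of 1 − 0.95⁷ = 30.2%, or roughly 23-29% with correlation. The documents do not support that figure as the error rate of the primary claim. No section defines a seven-test family: section 1.1 names only Cmax, Tmax and two example scales, and where the four subjective outcomes are listed they are secondary. The PK main effect and the subjective interaction are also separate questions, and an interaction on harshness cannot show that nicotine uptake differs.

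Finally, the preference for AUC can be challenged. Cmax and Tmax are the only PK outcomes in section 1.1, and rate of uptake is part of the rationale in section 2. That is a fair argument for keeping all three primary under a stated rule. It is not an argument for having no rule.

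**Conclusion.** The point holds in two parts. First, section 1.1 conflicts with sections 8.1, 8.2, 19.4 and 19.5, and it omits the one outcome on which section 19.1 sizes the trial. This rests on the text alone. Second, section 19.4 puts an either-or question to three PK outcomes without order or adjustment. The nominal 5% then becomes about 8-14%.

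That range rests on two assumptions: 0.05 per test, which is inferred, and correlations that the documents do not give. The 14.3% needs independence, which is unlikely for AUC and Cmax taken from the same curve. The low end needs Tmax to track both closely. No error in the sample-size arithmetic is claimed.

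**What to change.** 1. **Section 1.1:** add AUC(0-120) to the PK objective and move the flavor-by-salt item to a secondary objective. Section 1.1 then matches 8.1, 8.2, 19.4 and 19.5.
2. **Section 19.4:** state that the base effect is tested in a fixed order at two-sided 0.05, AUC first because section 19.1 is sized on it, then Cmax, then Tmax. Testing stops at the first non-significant result, and later outcomes are then reported as supportive with their intervals.
3. **Alternative:** keep the three outcomes on an equal footing and apply Holm. This is one acceptable choice among several. Its cost for AUC at the strictest step is 62.1% power under the simplified formula, or almost none if 500 is the within-subject SD and 18 people complete.

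Either rule should be written in before unblinding. The fixed order needs no extra participants and leaves AUC power unchanged. Its cost is that Cmax can be claimed only if AUC succeeds, and Tmax only if both do.

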4 LOCAL AND STUDY-WIDE NUMBER OF SUBJECTS

This is a single center study to be conducted at Roswell Park. The target accrual is 20 evaluable participants (participants who have completed all 4 study visits), with an equal number of males and females. Accrual is expected to take up to 4 years.

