10.1 Dosing and Administration

The device will be filled with either (1) free-based nicotine e-liquid solution of unflavored (2) free-based nicotine e-liquid solution of tobacco flavor (3) salt-based nicotine e-liquid solution of unflavored or (4) salt-based nicotine e-liquid solution of tobacco flavor. Both the study personnel and study participants will be blinded to the solution flavor and nicotine concentration. All e-liquids will contain 0.148M nicotine (24 mg/mL free-base nicotine or 24 mg/mL nicotine benzoate). Participants are randomized to the order of the e-liquids by the study statistician using the Williams Design; a special case orthogonal latin squares design generated using SAS v9.3.

Intervention will be administered on an outpatient basis. Reported adverse events (AEs) and potential risks are described in **Section 13** and **Section 17**.

Nicotine (3-(1-methylpyrrolidin-2-yl)-pyridine) the primary alkaloid in tobacco products binds stereo-selectively to nicotinic-cholinergic receptors on autonomic ganglia, the adrenal medulla, neuromuscular junctions and in the brain. Nicotine exerts two effects, a stimulant effect exerted at the locus ceruleus and a reward effect in the limbic system. Intravenous administration of nicotine causes release of acetylcholine, norepinephrine, dopamine, serotonin, vasopressin, beta-endorphin and ACTH. Nicotine is a highly addictive substance. Nicotine also induces peripheral vasoconstriction, tachycardia and elevated blood pressure. Nicotine replacement therapies (like inhalers and patches) are used to treat smoking withdrawal syndrome. Nicotine is classified as a stimulant of autonomic ganglia.

Electronic nicotine delivery systems (ENDS) usually look similar to regular cigarettes, cigars, pipes, or pens, but do not contain tobacco. Instead, they are comprised of a battery-powered atomizer that produces vapor for inhalation from solutions that contain nicotine. Electronic cigarettes (e-cigarettes) are the most popular ENDS on the market. Different ENDS brands are engineered differently. The differences include the appearance, the nature of nicotine solution, the capacity of the cartridge containing the solution, the nature of the heating element, and size and

Roswell Park Protocol No.: I 475819

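### The crossover models in 19.4 and 19.5 leave out a visit effect that the Williams design would let them remove; adding one costs about 0.1% in interval width and protects against a possible loss of precision.

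*Combined protocol and SAP*

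**What the plan says.** Section 10.1: "Participants are randomized to the order of the e-liquids by the study statistician using the Williams Design". Section 19.2 says the orders are random, "with a different randomization order for each participant", and adds on carry-over that "we will consider linear mixed models that will incorporate a carry-over effect".

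The primary model in 19.4 has base, flavor, "their interaction, prior combination indicator (for carry-over effect), and a random subject effect using a linear mixed model". The salt effect on AUC, Cmax and Tmax "will be evaluated using tests about the least square means of" base, with 95% confidence intervals for the differences. Section 19.5 repeats the model for the subjective outcomes: "Each outcome will be modeled as a function of base, flavor, their interaction, prior combination, and a random subject effect using a linear mixed model". The base-by-flavor interaction is then tested by an F-test; section 1.1 lists that interaction as a primary objective.

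No section adds a visit (period) term. None says how visit 1, which has no preceding liquid, is coded in the prior-combination term, or how carry-over is tested.

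On numbers, section 4 states: "The target accrual is 20 evaluable participants (participants who have completed all 4 study visits". Section 19.1 states that "a sample size of n=18 provides 80% power" for an AUC difference of 700 ng/mL × min with a within-patient SD of 500, and enrolls up to 20 to cover drop-out.

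**The concern.** A Williams design places each liquid equally often at each visit, so visit differences can be separated from liquid differences at almost no cost. That benefit is realised only if visit is in the model. Here the same device and tasks are repeated over four sessions, so a first-session effect or gradual drift is plausible. Without a visit term, such variation is partly or wholly counted as residual error.

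What is at stake is the width of the intervals promised in 19.4, sensitivity to salt effects smaller than 700, and the interaction test, whose standard error is twice that of the salt effect. Exact balance over visits also needs a multiple of four participants. The 18 in section 19.1 is not one, so with 18 completers an omitted visit effect no longer cancels exactly.

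**Working it through.** **Inputs.** From the plan: 20 participants × 4 visits = 80 rows; within-patient SD 500; planned difference 700; two-sided 5% level (19.1, section 4). Assumptions: visit effects of 100 or 200 per visit (linear drift, 0.2 or 0.4 SD), or a visit-1 shift of 250 or 500 (0.5 or 1 SD); no true carry-over. Subjects are fitted as fixed, which is the within-subject analysis.

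**1. The plan's own figure.** A two-sample t-test with 9 per group, difference 700 and SD 500 has 79.6% power, so n=18 is the total of two independent groups; 18/0.9 = 20. The crossover model is far more precise than that calculation.

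**2. Cost of the visit term.** For a Williams square used five times:

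| Model | Rank | Residual df | Variance factor, base | 95% half-width |
|---|---|---|---|---|
| Current, 'none' level at visit 1 | 27 | 53 | 0.055 | 235.2 |
| Current, visit 1 coded 0 | 26 | 54 | 0.055 | 235.1 |
| Visit added, prior term 3 df | 29 | 51 | 0.055 | 235.4 |

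SE = 500 × √0.055 = 117.3; half-width = SE × t. The interaction, as a difference of flavor effects, has factor 0.22 in all three, so its SE is twice as large. Five different Williams squares, which give 20 distinct orders and so let 10.1 and 19.2 both hold, give the same factors.

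**3. Loss if visit effects exist and visit is omitted.** Expected residual variance is multiplied by 1 + (20 × unabsorbed sum of squares per participant)/(500² × df).

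- *Visit 1 coded 0* (nothing absorbed). Drift 100: deviations −150, −50, 50, 150, sum of squares 50,000; 20 × 50,000/250,000 = 4; 1 + 4/54 = 1.074. Drift 200: 1 + 16/54 = 1.296. Shift 250: 250² × 0.75 = 46,875; 20 × 46,875/250,000 = 3.75; 1 + 3.75/54 = 1.069. Shift 500: 1 + 15/54 = 1.278.
- *'None' level* (absorbs visit 1 against the rest). A pure visit-1 shift costs nothing. Drift 100: deviations −100, 0, 100 over visits 2 to 4, sum of squares 20,000; 20 × 20,000/250,000 = 1.6; 1 + 1.6/53 = 1.030. Drift 200: 1 + 6.4/53 = 1.121.

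Square roots give the increase in SE. Power is shown for 700 and for an illustrative 350 (half the planned effect; not in the plan).

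| Coding and visit effect | SE increase | Power at 350 | Power at 700 |
|---|---|---|---|
| Visit fitted | 0 | 83% | >99.9% |
| 'None', drift 100 / 200 | 1.5% / 6% | 82% / 79% | ≥99.9% |
| Coded 0, drift 100 / 200 | 4% / 14% | 81% / 73% | ≥99.9% |
| Coded 0, shift 250 / 500 | 3% / 13% | 81% / 74% | ≥99.9% |

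Type I error for base without the visit term, at drifts 100 and 200, is 4.7% and 3.8% ('none') or 4.4% and 2.6% (coded 0). It falls below 5% rather than rising.

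**4. Eighteen completers.** Over all 190 ways of losing 2 of 20 participants, with drift 100, the bias in the salt contrast averages 0. Its mean absolute size is 6 to 7 (worst 21) with a 'none' level and 10 to 12 (worst 33) with visit 1 coded 0, against an SE of about 124. It is 0 once visit is fitted.

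**5. A separate matter: dropped rows.** If visit 1 were left blank in the prior term and software dropped those rows, 60 rows and 34 df would remain. The factor rises to 0.080, SE = 500 × √0.080 = 141.4, half-width 287, and 287/235 = 1.22. Adding visit to that reduced data set gives 288, so the visit term does not repair it; keeping the rows does.

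**6. Estimability.** With visit plus a five-level prior factor, 'none' is aliased with visit 1. The base difference stays estimable but the individual base least square means do not. With the 3-df coding (0 at visit 1) they are.

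**The case against.** The strongest reply is that nothing is shown to be lost. The plan gives no visit-effect size; every drift and shift above is an assumption. If there is no visit effect and visit-1 rows are kept, the current model is as precise as the amended one. A natural reading of an indicator for the prior liquid is a set of dummies that are all zero at visit 1, which is the 'none' coding, where the loss is at most 6% at the sizes tried. This stands, and it is why the point is about protection against a possible loss.

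It is also fair that section 4 aims for 20 completers, a multiple of four, and that even with 18 the chance bias is small against its SE. No power can be computed for the subjective outcomes, because the plan gives no SD or target for them; only the proportional loss in SE carries over.

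A reader might infer more, and the documents do not support it:

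- That the salt comparison is biased or its type I error inflated. With complete balanced data and visit 1 as 'none' or 0, neither is so.
- That the trial is underpowered for 700. Power is at least 99.8% in every case examined, including dropped rows.
- That omitting visit widens the interval by 22%. That figure belongs only to dropped visit-1 rows, which the plan nowhere announces. It also assumes subjects fitted as fixed; with random subjects, as 19.4 specifies, the SE increase is 17 to 21% depending on between-subject variance.
- That the wash-out check will mislead. A joint 4-df test including a 'none' level would give a false signal in 28% of trials at a shift of 250, but the plan specifies no such test and only says such models will be considered. A 3-df comparison among prior liquids does not over-reject.

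**Conclusion.** The omission is real: neither 19.4 nor 19.5 has a visit term, and no other section supplies one. Its consequence is conditional and modest. For drifts of 0.2 to 0.4 SD per visit or visit-1 shifts of 0.5 to 1 SD, the SE of the salt effect is 0 to 6% larger with a 'none' level and 3 to 14% larger with visit 1 coded 0. With 18 completers, fitting visit also removes a small chance bias. These sizes rest on the assumed visit effects, the SD of 500 from 19.1 and no true carry-over. The planned AUC conclusion and type I error are not threatened. The change should be made because it is standard for this design and nearly free, and because fixing the coding beforehand avoids a choice made after the data are seen.

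**What to change.** In 19.4 and 19.5:

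1. Add visit (four levels) as a fixed factor.
2. State that visit-1 rows are kept, and that prior combination is coded as 3 df among the four prior liquids (sum-to-zero, set to 0 at visit 1).
3. Assess carry-over by that 3-df comparison adjusted for visit, with estimates and confidence intervals.

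This is two sentences in 19.4 and one in 19.5. It costs 2 residual df against the 'none' coding (53 to 51) or 3 against zero coding (54 to 51). With no visit effect at all, the half-width goes from 235.1–235.2 to 235.4, about 0.1%, and power at 350 falls by less than 0.1 percentage point. Sample size, visits and conduct are unchanged.
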